3.4 Rationale for choice of comparator

This is a placebo controlled study. The use of a double blind placebo arm as a comparator is to provide a comparison group for an unbiased collection of safety and tolerability data.

Corporate Confidential Information

3.6 Risks and benefits

While patients who participate in the study may notice an improvement in their symptoms and/or lung function, this is not expected because of the exploratory nature of this study. QBW276 has been safe and well tolerated at doses examined and the risk/benefit assessment remains supportive for examination in patients with CF.

Corporate Confidential Information

The risk to patients in this trial will be minimized by adherence to the eligibility criteria, close clinical and laboratory monitoring, stopping rules and dosing well within the safety margins of the systemic exposure cap determined from pre-clinical toxicity studies. Patients will be closely monitored for changes in vital signs, serum electrolytes, ECG intervals and lung function. Plasma aldosterone will be monitored between cohorts during the study.

A maximum of 333 mL and 371 mL of blood is planned to be collected for Cohorts 1 and 2 over a period of 18 (+21) and 25(+21) days, respectively. A maximum of 421 mL of blood is planned to be collected over a period of 105 (+16) days in cohort 3. Additional samples for clinical monitoring of any abnormal laboratory values may be collected. This is not considered to be a risk for this population.

Women of child bearing potential should be informed that taking the study drug may involve unknown risks to the fetus if pregnancy were to occur during the study and agree that in order to participate in the study they must adhere to the pre-specified contraception requirement for the duration of the study and for at least 3 days after the last dose of the study drug or until the end-of-study visit, whichever occurs later. If there is any question that the patient will not reliably comply, they should not be randomized in the study.

Refer to exclusion criteria for further details in [Section 4.2](#).

There may be unknown risks of QBW276 which may be serious and unforeseen.

4 Population

The study population will be comprised of male and female patients aged 18 and above with a diagnosis of CF. Patients in cohort 3 will be restricted to those who are homozygous for the F508del mutation.

The investigator must ensure that all patients being considered for the study meet the following eligibility criteria. No additional criteria should be applied by the investigator, in order that the study population will be representative of all eligible patients.

Patient selection is to be established by checking through all eligibility criteria at screening and baseline. A relevant record (e.g. checklist) of the eligibility criteria must be stored with the source documentation at the study site.

Deviation from **any** entry criterion excludes a patient from enrollment into the study.

4.1 Inclusion criteria

Patients eligible for inclusion in this study have to fulfill all of the following criteria:

1. Written informed consent must be obtained before any assessment is performed.
2. Male and female patients of age 18 and above with a confirmed diagnosis of CF, all mutations as per the Cystic Fibrosis Foundation consensus guidelines ([Farrell et al 2008](#)).
3. For Cohort 3, male and female patients of age 18 and above with a confirmed diagnosis of CF, who are homozygous for the F508del mutation.
4. Should be on stable medical regimen in the 4 weeks prior to screening and baseline visits (Cohorts 1 & 2: Screening; Cohort 3: Screening (v1) and Baseline (v2)).
5. Should be established as "clinically stable to participate in the study" in the judgment of a site investigator at the screening and baseline visit.
6. FEV₁ must be between 40 and 100% predicted (inclusive) by NHANES/Hankinson standards at screening and baseline visits (may be repeated once at screening and once at baseline) (Cohorts 1 & 2: Screening; Cohort 3: Screening (v1) and Baseline (v2)).
7. LCI_{2.5}≥ 8 at screening if FEV₁ > 80% (Cohorts 1 & 2 only).

8. Must pass the metabolite screening assay prior to baseline visit.
9. Must demonstrate ability to communicate well with the investigator, to understand and comply with the requirements of the study.

4.2 Exclusion criteria

Patients fulfilling any of the following criteria are not eligible for inclusion in this study. No additional exclusions may be applied by the investigator, in order to ensure that the study population will be representative of all eligible patients.

1. Use of other investigational drugs at the time of enrollment, or within 5 half-lives of enrollment, or within 30 days, whichever is longer; or longer if required by local regulations. The only exception to this is QBW276. If a patient has participated in cohort 1 of CQBW276X2201, he or she will qualify to participate in cohort 2 contingent up on approval from the sponsor, as long as he/she has been though a 4 week wash-out between dosing in the two cohorts, and has not experienced any significant AEs since enrollment in cohort 1. This will ensure that no patient receives more than 4 weeks of the investigational drug QBW276 in his lifetime until further supportive toxicology studies are conducted in the drug's development program. Note that patients who participate in cohorts 1 or 2 cannot participate in cohort 3.
2. History of significantly uncontrolled or untreated cardiovascular, adrenal or electrolyte abnormalities.
3. History of malignancy of any organ system (other than localized basal cell carcinoma of the skin), treated or untreated, within the past 5 years, regardless of whether there is evidence of local recurrence or metastases.
4. History of lung transplant.
5. Pregnant or nursing (lactating) women, where pregnancy is defined as the state of a female after conception and until the termination of gestation.
6. A history of clinically significant ECG abnormalities, or any of the following ECG abnormalities at screening or baseline visits:
 - PR > 200 msec
 - QRS complex > 120 msec
 - QTcF > 450 msec (males)
 - QTcF > 460 msec (females).
7. History of adverse reaction or hypersensitivity to any of the study drugs, excipients (e.g. lactose) or to drugs of similar chemical classes, such as amiloride.
8. Any upper respiratory tract infection (e.g. common cold, influenza, sinusitis) or signs or symptoms thereof within 4 weeks prior to dosing that, in the opinion of the investigator, may jeopardize the patient or the study data in case of the patient's participation in the study.
9. Clinical evidence of liver disease or liver injury as indicated by clinically significant abnormal liver function tests as judged by the investigator, such as SGOT, SGPT, GGT, alkaline phosphatase, or serum bilirubin at screening or baseline visits.

10. Clinical evidence of significantly impaired renal function (i.e., CLr <30 mL/min) as indicated by abnormal creatinine or BUN values or clinically significant abnormal urinary constituents (e.g., albuminuria) at screening or baseline visits.
11. Women of child-bearing potential, defined as all women physiologically capable of becoming pregnant, unless they are using highly effective methods of contraception for the duration of the study and for at least 3 days after the last dose of the study drug or until the end-of-study visit, whichever occurs later.

Highly effective contraception methods include:

- Total abstinence (when this is in line with the preferred and usual lifestyle of the patient). Periodic abstinence (e.g. calendar, ovulation, symptothermal, post-ovulation methods) and withdrawal are not acceptable methods of contraception.
- Female sterilization (have had surgical bilateral oophorectomy with or without hysterectomy) or tubal ligation at least six weeks before taking study treatment. In case of oophorectomy alone, only when the reproductive status of the woman has been confirmed by follow up hormone level assessment.
- Male sterilization (at least 6 m prior to screening). For female patients in the study, the vasectomized male partner should be the sole partner for that patient.
- Use of oral, injected or implanted combined hormonal methods of contraception or placement of an intrauterine device (IUD) or intrauterine system (IUS) or other forms of hormonal contraception that have comparable efficacy (failure rate <1%), for example hormone vaginal ring or transdermal hormone contraception.

In case of use of oral contraception women should have been stable on the same pill for a minimum of 3 months before taking study treatment.

Women are considered post-menopausal and not of child-bearing potential if they have had 12 months of natural (spontaneous) amenorrhea with an appropriate clinical profile (e.g. age appropriate, history of vasomotor symptoms) or have had surgical bilateral oophorectomy (with or without hysterectomy) or tubal ligation at least six weeks prior to enrollment. In the case of oophorectomy alone, only when the reproductive status of the woman has been confirmed by follow up hormone level assessment is she considered not of child-bearing potential.

12. Smokers (use of inhaled tobacco products in the previous 3 months). Urine cotinine levels will be measured during screening and at baseline for all patients. Smokers will be defined as any patient who reports inhaled tobacco use in the previous 3 months and/or who has a urine cotinine ≥ 500 ng/mL. (E-cigarettes and nicotine patches are considered permitted concomitant medications).
13. Sexually active males unless they agree to use a condom during intercourse for the duration of the study and for at least 3 days after the last dose of the study drug or until the end-of-study visit, whichever occurs later, and agree to not father a child in this period. A condom is required to be used also by vasectomized men in order to prevent delivery of drug via seminal fluid.
14. Recent (within the last one year) and/or recurrent history of autonomic dysfunction (e.g., recurrent episodes of fainting, palpitations, etc.).

15. A positive HIV, Hepatitis B Ag or Hepatitis C Ab test result (Unless previously treated and confirmed Hepatitis C cleared).
16. History of drug or alcohol abuse within the 12 months prior to dosing, or evidence of such abuse as indicated by the laboratory assays conducted during screening and baseline visits.
17. Any changes in concomitant medications during the 4-week prior to screening and baseline visits. Over-the-counter oral and topical medications, such as paracetamol/acetaminophen, antihistamines, etc may be used in line with the product labels.
18. Patients on Prohibited medications as listed in [Section 5.2](#) of the study protocol and in the 'Guidance for Prohibited and Concomitant Medications' provided in the SOM, will be excluded from the study.

Note: In the case where a safety laboratory assessment at screening and/or initial baseline is outside of the normal range and considered clinically significant, the assessment may be repeated once prior to randomization. Non-clinically significant abnormal values need not be repeated if this is deemed appropriate by the investigator.

No additional exclusions may be applied by the investigator, in order to ensure that the study population will be representative of all eligible patients.

5 Restrictions for Study Patients

During recruitment, screening/informed consent review, and baseline visit, the patients must be informed and reminded of the following restrictions:

5.1 Contraception requirements

Please refer to exclusion criteria ([Section 4](#)) for details of contraception requirements for the study.

5.2 Prohibited treatment and rescreening

If a patient experiences a respiratory infection or exacerbation which requires systemic antibiotics and/or systemic glucocorticoids at any time, he/she will be discontinued from the study. He/she may be rescreened if he/she subsequently fulfills the required inclusion/exclusion criteria for the study. Note that chronic inhaled and/or systemic antibiotics are permitted as concomitant medications during the study, if they are considered the patient's standard of care at screening and baseline visits.

If a patient is deemed a screened failure, he/she maybe rescreened once based on the investigator's judgement.

Patients who have failed to meet ATS requirements for acceptability/reproducibility for Spirometry or MBNW (Cohorts 1 & 2), will be allowed one additional repeat testing session at Screening and/or Baseline in order to meet inclusion criteria. For additional details on rescreening and retesting, please refer to the site operations manual (SOM).

Patients should refrain from using their short and long acting bronchodilators for 6, 12 or 24 hours as described in the site operations manual (SOM) to enable measurement of trough

lung function. If the patient is not able to withhold rescue medications due to bothersome symptoms, the patient may be rescheduled if deemed appropriate by the investigative site.

Butylcholinesterase and acetylcholinesterase inhibitors are prohibited because QBW276 is hydrolyzed mainly by butylcholinesterase and acetylcholinesterase enzymes. Patients who are either on these inhibitors or patients who fail the butylcholinesterase screening assay will be excluded from the study. The following butylcholinesterase and acetylcholinesterase inhibitors are prohibited:

- Aclidinium bromide
- Amitriptyline
- Citalopram
- Donepezil
- Ecothiopate
- Galantamine
- Lovastatin
- Neostigmine
- Rivastigmine
- Simvastatin
- Sertraline
- Tacrine

Patients who are prescribed these medications during the course of the study should be immediately discontinued from the study and the Sponsor must be informed. The list of prohibited medications is not inclusive and subjects may be exposed to non-medicinal butyrylcholinesterase inhibitors, such as insecticides, which should be monitored.

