as long as the systemic exposure cap based on pre-clinical data or a clinical maximum tolerated dose (MTD) is not exceeded. Cohorts 1 and 2 will enroll 8 patients each, with 6 patients randomized to receive active drug and 2 patients randomized to receive matching placebo. Cohort 1 will be dosed for 1 week while cohort 2 will be dosed for 2 weeks. Cohort 2 will be initiated only after cohort 1 has completed dosing. Cohort 2 may be skipped if safety, tolerability, PK and PD data from cohort 1 are found favorable to proceed directly to cohort 3. In cohorts 1 and 2, patients may be replaced if they do not complete the study duration for reasons other than safety to obtain 8 completers in each cohort. If a patient has participated in cohort 1, he/she may qualify to participate in cohort 2 contingent upon approval from the sponsor, as long as he/she has been through a 4 week wash-out between dosing in the two cohorts, and has not experienced any significant AEs since enrollment in cohort 1. This will ensure that no patient receives more than 4 weeks of the investigational drug QBW276 in his/her lifetime until further supportive toxicology studies are conducted in the drug's development program.

NOTE: No patient randomized to cohort 1 or 2 will be eligible for cohort 3.

Cohort 1 and 2

Cohorts 1 and 2 will consist of a 21 day screening period followed by a baseline visit and a 7 or 14 day Treatment Period in cohort 1 and 2, respectively. Adequate windows will be provided for patient's convenience. QBW276 will be administered on top of the patient's usual standard of care medications.

Study inclusion/exclusion criteria as well as medication use will be assessed at screening. Patients who meet the inclusion/exclusion criteria at screening will report to the study site on Day -1 at a time specified by the investigator, for the baseline assessments. All baseline safety evaluation results must be available prior to dosing on Day 1, hence, Day -1 assessments can be carried out up to 72 hours prior to Day 1 dosing.

Patients who meet all of the inclusion and none of the exclusion criteria at baseline will then report to the study site on Day 1 and will remain in the clinic until at least 6 hours after the first dose in the morning.

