For Cohort 3, patients will be randomized to one of two treatment sequences: QBW276 in Period 1 and Placebo in Period 2 or Placebo in Period 1 and QBW276 in Period 2. Based on drop-out rates observed during conduct of the study, up to 40 patients will be randomized to ensure that at least 24 patients complete the study. After a 45 day screening period, patients who meet all inclusion and exclusion criteria will receive drug for 4 weeks and placebo for 4 weeks, separated by a washout period of approximately 3 to 4 weeks in patients who cycle inhaled antibiotics. Washout period may be shortened to 2 weeks in patients who do not cycle inhaled antibiotics. QBW276 will be administered on top of the patient's usual standard of care medications. For patients on cyclic inhaled antibiotics, baseline for periods 1 and 2 will commence on approximately day 7 (0/+3) of the patient's standard of care cyclic inhaled antibiotic regimen. Patients who use the same inhaled antibiotic throughout the year may start the study on any antibiotic day.

Screening and baseline visits for cohort 3 will be similar to the respective visits in cohorts 1 and 2. On Day 1 of cohort 3, pre-dose safety, efficacy Corporate Confidential Information will be performed. Following the pre-dose procedures eligible patients will be dosed for up to 28 days. Post-dose evaluations will include routine safety evaluations and blood for PK assessments. The patients will be asked to return to the study site for follow-up visits on Days 7, 14, 21, and 28 after which they will undergo an approximately 3 to 4 week wash-out period (may be shortened to 2 weeks in patients who do not cycle inhaled antibiotics) prior to cross-over to the opposite arm, and follow a similar visit schedule until End of Study assessment approximately 7 days after the last visit in the second period. All patients will undergo the same assessments regardless of their dose.

Efficacy will be evaluated by spirometry and responses to the respiratory domain of the CFQ-R. Safety will be monitored by assessment of vital signs, physical examination, ECG, clinical laboratory evaluations (hematology, blood chemistry, and urinalysis), urine electrolytes, aldosterone in plasma, and monitoring of adverse events (AEs) throughout the study.

Corporate Confidential Information

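### Section 5.2 allows rescreening after a treated infection or exacerbation, and no visible criterion bars a patient already dosed in Cohort 3 from re-entering it: a completed re-entry would give 29 to 56 days of QBW276 against a 28-day lifetime limit

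*Protocol*

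**What the plan says.** Section 5.2 of the protocol states that for a "respiratory infection or exacerbation which requires systemic antibiotics and/or systemic glucocorticoids at any time, he/she will be discontinued from the study". The next sentence permits return: "He/she may be rescreened if he/she subsequently fulfills the required inclusion/exclusion criteria for the study". Screen failures have a rule of their own in the same section: "If a patient is deemed a screened failure, he/she maybe rescreened once". For further rescreening detail, 5.2 points to the site operations manual (SOM).

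The exposure limit is in Section 3.1 and again in exclusion 1 of Section 4.2. The conditions for moving from Cohort 1 to Cohort 2 are said to ensure that "no patient receives more than 4 weeks of the investigational drug QBW276 in his/her lifetime until further supportive toxicology studies are conducted". Exclusion 1 exempts QBW276 from its ban on recent investigational drugs, describes the sponsor-approved route from Cohort 1 to Cohort 2, and closes with one bar on Cohort 3: "Note that patients who participate in cohorts 1 or 2 cannot participate in cohort 3".

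For Cohort 3, Section 3.1 says that "patients who meet all inclusion and exclusion criteria will receive drug for 4 weeks and placebo for 4 weeks", and that "up to 40 patients will be randomized to ensure that at least 24 patients complete the study". Section 7.1 says that a patient with an exacerbation is to be discontinued and can be replaced. It does not mention re-entry. Section 1.4 of the SAP repeats the 4-week limit and is silent on rescreening.

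**The concern.** The 5.2 trigger is not confined to screening. It applies whenever the event happens and ends study participation, so it covers patients already taking study drug. Because screen failures are handled separately, the permission to rescreen cannot be meant for them alone. It depends only on meeting the entry criteria and, unlike the screen-failure rule, has no limit on the number of attempts.

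The 4-week limit is tied to the toxicology package, so it protects patients. A rule elsewhere in the same protocol that lets a patient start a second active course would undercut it. Blinding adds a difficulty. After an exit in Period 1 or washout, the site does not know whether the patient has had QBW276 or placebo, so a bare reminder of the limit does not tell the site which patients it affects.

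**Working it through.** **Inputs.** Limit: 4 weeks = 4 × 7 = 28 days (Sections 3.1 and 4.2). Nominal active courses: Cohort 1, 7 days; Cohort 2, 14 days; Cohort 3, 28 days (Section 3.1). Let d be the QBW276 days taken before exit, from 0 to 28. The documents do not predict d.

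**Step 1: the plan's own claim, without re-entry.**
- Cohort 1 then Cohort 2: 7 + 14 = 21 days. With the +2-day windows on the Day 7 and Day 14 visits, 9 + 16 = 25. Both are within 28.
- One Cohort 3 pass: 28 days. Headroom is 28 − 28 = 0.

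So the limit holds as designed, but Cohort 3 leaves nothing spare.

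**Step 2: does any visible criterion stop a dosed Cohort 3 patient returning to Cohort 3?**
- Exclusion 1 exempts QBW276. Even if earlier Cohort 3 dosing were counted, that exclusion is a time-limited washout (the longer of 5 half-lives and 30 days, or longer under local rules). It would delay re-entry but not limit cumulative days.
- The closing note of exclusion 1 names Cohorts 1 and 2 only.
- The 4-week criteria on stable regimen, concomitant medication and recent respiratory infection also only delay.
- Stopping rule (c) in Section 7.5 concerns systemic exposure (AUC), not duration.
- Section 7.1 offers replacement and adds no bar.

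**Step 3: total exposure with one completed re-entry, T = d + 28.**

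| Exit from first pass | d | T (days) |
|---|---|---|
| After placebo only | 0 | 28 (no breach) |
| Active Day 1 | 1 | 29 |
| Active Day 7 | 7 | 35 |
| Active Day 14 | 14 | 42 |
| Active Day 21 | 21 | 49 |
| Active Day 27 | 27 | 55 |
| Washout or Period 2, after active Period 1 | 28 | 56 (56/28 = 2.0 times the limit) |

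A patient who exits after any Period 2 dosing always has d of at least 1. For Period 1 and washout exits, d exceeds 0 with probability 1/2 if the two sequences are allocated 1:1. That ratio is an assumption, since it is not visible.

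**Step 4: incomplete re-entry and missed doses.** The active days still available on re-entry are 28 − d: 27, 21, 14, 7 and 0 for d = 1, 7, 14, 21 and 28. The limit is passed only if re-entry dosing goes beyond that. Section 7.1 stops Cohort 3 treatment at 8 or more missed doses, between visits or consecutively. Assuming twice-daily dosing:
- 7 missed doses on re-entry are 7/2 = 3.5 days, so T = d + 24.5: 25.5 at d = 1, 28.5 at d = 4 and 52.5 at d = 28. The limit is passed from d = 4.
- As an extreme, 7 missed in each of four visit intervals is 28 doses, or 14 days, so T = d + 14: 29 at d = 15 and 42 at d = 28. The limit is passed from d = 15.

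**Step 5: Cohorts 1 and 2, nominal lengths.** Cohort 1 repeated: at most 7 + 7 = 14. Cohort 2 repeated: at most 14 + 14 = 28. Neither exceeds the limit. Cohort 1, then Cohort 2, then Cohort 2 again: up to 7 + 14 + 14 = 35, which does. The Cohort 2 result has no slack: using the +2-day window in both passes would give 16 + 16 = 32.

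**The case against.** The best defence is that the limit is already inside the criteria that govern rescreening. Exclusion 1 states the lifetime maximum and describes only one route to further QBW276, from Cohort 1 to Cohort 2 with sponsor approval. A site could reasonably take that as the only re-exposure allowed. This has some force. But the sentence presents the maximum as a result of the Cohort 1-to-2 conditions, not as a condition that a patient must satisfy, and it does not mention earlier Cohort 3 dosing. Section 4.2 also forbids investigators to add exclusions, which leaves a cautious site on uncertain ground.

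Second, rescreening is not re-dosing. No visible sentence says that a randomized patient may be randomized again, Section 7.1 speaks of replacement, and the SOM and IRT may prevent a second assignment. This stands as a limit on the finding: the route exists by implication. A reader might infer that the protocol expressly authorises a second 28-day course, and it does not.

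Third, a reader might infer that a blinded site could not respect the limit at all. That goes too far. Re-entry is optional, and a site could treat every dosed patient as possibly exposed without breaking the blind. The text simply does not tell it to.

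Fourth, a reader might extend the concern to every cohort. Step 5 does not support a general bar: at nominal lengths, a repeat within Cohort 1 alone or Cohort 2 alone stays within 28 days.

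**Conclusion.** The point holds for Cohort 3. On the visible text, a patient dosed in Cohort 3 and then discontinued under 5.2 can be rescreened for Cohort 3, and with any earlier QBW276 days a completed second active period passes the 4-week limit. For one re-entry the excess over 28 days equals d, from 1 to 28 days. Patients who had taken placebo only are unaffected.

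This rests on three assumptions: that rescreening can lead to a second randomization, that neither the SOM nor IRT blocks it, and that the toxicology condition on the limit has not been lifted. Parts of the protocol are redacted, so the claim is that there is no visible bar, not that none exists. The documents do not say how many patients would re-enter. The 56-day figure is the worst case for one re-entry and not an expected outcome. Confidence is medium, but a rule that can defeat a stated safety limit should be corrected at the next amendment.

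**What to change.** Add this sentence to Section 5.2, to exclusion 1 in Section 4.2, and to the synopsis:

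> A patient who has taken any dose of study drug (QBW276 or placebo) in Cohort 3 may not be rescreened or re-randomized, but may be replaced (Section 7.1).

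Rescreening before the first dose is unaffected. The any-dose wording matters. An IRT check on active days alone would disclose the earlier treatment in Period 1 and washout exits, since acceptance would mean placebo and refusal would mean QBW276.

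Repeats within Cohort 1 alone or Cohort 2 alone need no bar, provided that a repeated Cohort 2 course keeps to its nominal 14 days. Add to exclusion 1 that a patient dosed in both Cohorts 1 and 2 does not repeat Cohort 2.

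The cost is wording in three places, with no new visits or CRF fields. The downside is that Cohort 3 patients who left after placebo only, and who would have stayed at 28 days, also lose re-entry. They can be replaced within the existing ceiling of 40 randomized. If the SOM already bars re-entry, the amendment only brings the protocol into line with it.
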